#### **7.1.2. FDG-PET/CT and CCTA Imaging**

FDG-PET/CT and CCTA imaging will be performed in randomized subjects at the day 1 visit and again at the day 184.

Participants will have PET imaging after an overnight fast to reduce myocardial FDG uptake. PET imaging will be done 3 hours after administration of 10 mCi of fluorine-18-labelled FDG.

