## Study Design

This study is a Phase 3, double blind, placebo-controlled, randomized, parallel group study, designed to compare the efficacy and safety of bococizumab 150 mg subcutaneously every 2 weeks to bococizumab placebo subcutaneously every 2 weeks for LDL-C lowering in HIV-infected subjects. The study will enroll approximately 200 subjects in 2 treatment arms, randomized 1:1 to either bococizumab or placebo injections. Randomized subjects will receive study drug for 52 weeks. The primary comparison of interest is bococizumab 150 mg compared to placebo. Rates of discontinuation due to AEs and SAEs will be described for both treatment groups.

After providing informed consent at the screening visit, subjects will be assessed to determine eligibility for the trial. Eligible subjects will be considered enrolled and progress to the Baseline visit. Results from screening evaluations will be reviewed and only subjects who continue to meet all eligibility criteria will be randomized. Randomized subjects will enter the 52-week treatment period, followed by a 6-week follow-up, for a total of 58 weeks study participation. Subjects will attend clinic visits as shown in the Schedule of Activities. Lipid levels will be blinded to the investigator and staff, subject and sponsor.

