## **SCHEDULE OF ACTIVITIES**

The Schedule of Activities table provides an overview of the protocol visits and procedures. Refer to STUDY PROCEDURES and ASSESSMENTS sections of the protocol for detailed information on each procedure and assessment required for compliance with the protocol.

The investigator may schedule unplanned visits in addition to those listed on the schedule of activities, in order to conduct evaluations or assessments required to protect the wellbeing of the subject

Study Phase	Screen	Rand	Treatment								Follow- Up
Protocol Activity (Week)	-8	0	4	8	12	24	30	40	52/EOS a		58
Visit Day	-57	1	29	57	85	169	211	281	365		407
Informed consent	X										
CV risk factors, demographics, medical history	X										
Vital Signs (HR, BP, temperature)	X	X	X	X	X	X	X	X	X		X
Height and weight		X				X		X	X		X
Physical examination	X					X		X	X		X
Prior Medications	X										
Concomitant medication		X	X	X	X	X	X	X	X		X
Adverse events		X	X	X	X	X	X	X	X		X
ECG	X					X					X
Review inclusion/exclusion criteria	X	X									
Laboratory											
Fasting Lipid Profile	X	X	X	X	X	X	X	X	X		X
Diet and contraception advice	X	X	X	X	X	X	X	X	X		X
Instruction on self-injection	X	X									
Randomization		X									
Dispense study treatment		X	X	X	X	X	X	X			
Brachial artery FMD		X,X				X					
FDG-PET/CT			X b				X b				
Coronary CT angiography			X b							X b	

a. EOS = End of Study, procedures to be completed for subjects who have early study discontinuation. Visit day 365/EOS will usually require 2 days to complete because of the requirement to perform coronary CT angiography study

b. FDG-PET/CT or coronary CT angiography reimage within 7 days if deemed necessary

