#### **2.2.7. Coronary CT Angiography Endpoints**

- Change in non-calcified plaque from baseline to follow-up study at 52 weeks.
- Change in high-risk plaque from baseline to follow-up study at 52 weeks.
- Incidence of new lesions from baseline to follow-up study at 52 weeks.
- Correlations between change in LDL-C and

- (a) change in volume of non-calcified coronary plaque
- (b) change in high-risk coronary plaque

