## **6.2. Treatment Period**

### **6.2.1. Visit Day 1**

Visit day 1 will usually require up to 7 days to complete because of the requirement to perform the brachial artery reactivity flow-mediated dilation, coronary CT angiography, and FDG-PET/CT studies after randomization and before the first treatment.

A qualified FDG-PET/CT and coronary CT angiography interpreter will measure the images. Study drug dispensing will be delayed until after the repeat scan is completed.

Randomization:

Perform brachial artery reactivity flow-mediated dilation study;

Perform FDG-PET/CT imaging;

Perform coronary CT angiography;

Drug dispensation and dosing:

Instruct subject to self-inject;

Assessment during and after subject self-injection or injection by trained study nurse:

Provide lifestyle and contraception recommendations (Section 4.4.1);

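### Section 7.1.2 sets one follow-up day (184) for both FDG-PET/CT and coronary CT angiography, which fits neither the 52-week CCTA endpoints nor the 24-week PET endpoint

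*Combined protocol and SAP*

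**What the plan says.** The assessment section for imaging, 7.1.2, covers both modalities in one sentence: "FDG-PET/CT and CCTA imaging will be performed in randomized subjects at the day 1 visit and again at the day 184".

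The CCTA endpoints in section 2.2.7 are set at a different time. The first reads "Change in non-calcified plaque from baseline to follow-up study at 52 weeks", and the other two measured there, on high-risk plaque and on newly appearing lesions, carry the same 52-week time.

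Footnote a of the Schedule of Activities agrees with 2.2.7: "Visit day 365/EOS will usually require 2 days to complete because of the requirement to perform coronary CT angiography study". Section 1.2.4 also discusses plaque change over the 52-week treatment period, and it labels the CCTA endpoints exploratory.

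For PET, sections 2.2.6 and 9.2.5 both define the endpoint at 24 weeks.

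On which text governs, the Study Design sections (Protocol Summary and section 3) say: "Subjects will attend clinic visits as shown in the Schedule of Activities". The Schedule in turn points the other way for detail: "Refer to STUDY PROCEDURES and ASSESSMENTS sections of the protocol for detailed information on each procedure and assessment required for compliance".

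**The concern.** Two scans with endpoints 28 weeks apart (52 − 24) cannot share one follow-up day, and the day given belongs to neither. The larger conflict is for CCTA, where 7.1.2 would bring the follow-up scan forward to about half the interval that 2.2.7 requires.

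Three readings are open to a site:

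- **Follow 7.1.2 and overlook footnote a.** No week-52 CCTA is obtained, and it cannot be recovered later. The 2.2.7 endpoints cannot be computed as defined for those subjects. The planned correlations of plaque change with FDG uptake and LDL-C (2.1.5, 2.2.7) would rest on a different interval.
- **Follow both texts.** Each subject has an additional contrast CT that no endpoint uses.
- **Follow the Schedule.** CCTA is done at day 365, as 2.2.7 needs, but 7.1.2 is then not complied with.

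If sites differ, the CCTA data set would mix scans at about 26 and 52 weeks.

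**Working it through.** **Inputs.** Week and day labels come from the Schedule of Activities; visit days from 6.2.2; the imaging day from 7.1.2; endpoint weeks from 2.2.6, 2.2.7 and 9.2.5; the re-imaging allowance (7 days) from Schedule footnote b. The X marks in the Schedule's imaging rows are displaced in the text available for review and are not used.

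**Step 1: the plan's own calendar.** With day = 7 × week + 1, every visit from week 0 onwards is reproduced:

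| Week | 0 | 4 | 8 | 12 | 24 | 30 | 40 | 52 | 58 |
|---|---|---|---|---|---|---|---|---|---|
| 7 × week + 1 | 1 | 29 | 57 | 85 | 169 | 211 | 281 | 365 | 407 |
| Schedule day | 1 | 29 | 57 | 85 | 169 | 211 | 281 | 365 | 407 |

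So week 24 is day 169 and week 52 is day 365.

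**Step 2: place day 184.** (184 − 1)/7 = 26.1 weeks. It is not among the visit days. The nearest are day 169 (184 − 169 = 15 days earlier) and day 211 (211 − 184 = 27 days later).

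**Step 3: compare with the endpoints.**

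| Scan | Endpoint week | Endpoint day | Day in 7.1.2 | Difference |
|---|---|---|---|---|
| CCTA | 52 | 365 | 184 | 365 − 184 = 181 days early |
| PET | 24 | 169 | 184 | 184 − 169 = 15 days late |

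As a share of the CCTA interval: (184 − 1)/(365 − 1) = 183/364 = 0.503, or 50%.

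**Step 4: do the stated tolerances cover the gap?**

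- CCTA: the heading of 6.2.3 allows ±3 days, so the window opens on day 365 − 3 = 362, still 362 − 184 = 178 days after day 184.
- PET: a ±7-day window for the day-169 visit appears in the table of contents only. It ends on day 169 + 7 = 176. Adding the re-imaging allowance gives 176 + 7 = 183, one day short of day 184.

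**Step 5: does section 6 settle it?** Section 6.2.1 lists the baseline scan ("Perform coronary CT angiography"). The list for visit days 29 to 281 in 6.2.2 names no follow-up PET, and the day-365 list in 6.2.3 does not name CCTA. Section 6 therefore supports neither time.

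**The case against.** The strongest reply is that the intended CCTA time is easy to recover. Sections 2.2.7 and 1.2.4 and footnote a all point to week 52, and only one sentence says otherwise. Visits follow the Schedule, and 7.2.1, 7.2.3 and 7.2.4 defer to it for timing. The Schedule's reference to the assessment sections can be read as covering procedural detail rather than dates. The section 6 lists are visibly abridged, so their silence proves little. This is fair, and the text does lean towards day 365. But 7.1.2 does not defer to the Schedule: it states its own day, and it is the section to which the Schedule sends readers for imaging. No rule says which prevails.

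For PET, the 15 days are counted from visit day 1, whereas 6.2.1 allows up to 7 days to complete that visit and footnote b allows re-imaging within 7 days. If both were used in full (an assumption), baseline imaging would fall at about day 1 + 7 + 7 = 15, and day 184 would be (184 − 15)/7 = 24.1 weeks after it. The scan-to-scan interval could thus run from about 24.1 to 26.1 weeks. The documents do not give this as the reason for day 184. The PET discrepancy is therefore small, and such a scan would probably still be usable. The same allowance does nothing for CCTA, since it shortens the interval further below 52 weeks.

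Finally, the harm needs a site to arrange imaging on a day with no scheduled visit and to overlook footnote a. Nothing shows that this is likely, and the endpoints are exploratory.

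**Conclusion.** The contradiction is real and should be corrected. As written, 7.1.2 places the follow-up CCTA 181 days before the 52-week time in 2.2.7 and footnote a, at 50% of the defined interval, and no stated window accounts for it. The PET mismatch (15 days after day 169) is minor, but it means that the single day in 7.1.2 is right for neither scan.

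The consequence is confined to the exploratory imaging endpoints. No loss of power and no bias between arms is claimed, and the primary, key secondary and safety analyses do not depend on it. The result rests on the Schedule's week-to-day rule, which reproduces all nine visits from week 0 to week 58, and on complete sentences in the protocol rather than the damaged table cells.

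**What to change.** Split 7.1.2 by modality and reconcile it with 2.2.6, 2.2.7, 9.2.5, 6.2.3 and the Schedule of Activities, so that each scan has one follow-up time equal to the week in its endpoint definition.

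- If week 52 stands for CCTA, name day 365 in 7.1.2 and list CCTA among the procedures in 6.2.3.
- If week 24 stands for PET, name day 169 in 7.1.2.

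If the endpoint weeks stand, the cost is protocol wording in 7.1.2 and 6.2.3, with no extra scans, visits or patients.

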#### **7.1.3. Brachial Artery FMD**

The imaging will be done at the primary location of our study team. Analysis of digitized images is performed using dedicated software.

#### **7.1.4. Inflammatory Markers**

We will measure inflammatory markers including IL-6, hsCRP, fibrinogen and sCD14, a receptor for endotoxin, using well validated assays. Samples will be collected at the randomization visit and at the week 24/end of study visit.

## **7.2. Safety**

### **7.2.1. Laboratory**

Laboratory tests for safety will be performed at times defined in the Schedule of Activities of this protocol.

### **7.2.2. Cardiovascular Risk Factors and Medical History**

Cardiovascular risk factors and CV medical history will be collected through a dedicated case report form (CRF).

### **7.2.3. 12-Lead ECG**

A 12-lead ECG will be obtained at time points indicated in the Schedule of Activities. ECGs will be kept at the study site as part of subject's records. Clinically significant abnormalities present at baseline will be recorded on the medical history CRF. Additional ECGs may be performed for the evaluation of adverse events at the discretion of the investigator. Clinically significant abnormal findings occurring after baseline should be captured in the adverse event (AE) CRF.

### **7.2.4. Vital Signs**

Temperature, heart rate (HR) and BP will be measured at times specified in the Schedule of Activities.

### **7.2.5. Adverse Events**

All AEs will be recorded in the AE CRF from the time the subject receives the first dose of study drug to the end of study visit.

## **8. ADVERSE EVENT REPORTING**

### **8.1. Adverse Events**

All observed or volunteered AEs regardless of treatment group or suspected causal relationship to the investigational product will be reported as described in the following sections.

For all AEs, the investigator must pursue and obtain information adequate both to determine the outcome of the AE and to assess whether it meets the criteria for classification as a serious adverse event (SAE) requiring immediate notification to Pfizer or its designated representative. For all AEs, sufficient information should be obtained by the investigator to determine the causality of the AE. The investigator is required to assess causality. Follow-up by the investigator may be required until the event or its sequelae resolve or stabilize at a level acceptable to the investigator, and Pfizer concurs with that assessment.

### **8.2. Abnormal Test Findings**

The criteria for determining whether an abnormal objective test finding should be reported as an AE are as follows:

- Test result is associated with accompanying symptoms; and/or
- Test result requires additional diagnostic testing or medical/surgical intervention; and/or
- Test result leads to a change in study dosing or discontinuation from the study, significant additional concomitant drug treatment, or other therapy; and/or
- Test result is considered to be an AE by the investigator or sponsor.

Merely repeating an abnormal test, in the absence of any of the above conditions, does not constitute an AE. Any abnormal test result that is determined to be an error does not require reporting as an AE.

### **8.3. Serious Adverse Events**

An SAE is any untoward medical occurrence at any dose that:

- Results in death;
- Is life-threatening (immediate risk of death);
- Requires inpatient hospitalization or prolongation of existing hospitalization;
- Results in persistent or significant disability/incapacity (substantial disruption of the ability to conduct normal life functions);
- Results in congenital anomaly/birth defect.

Medical and scientific judgment is exercised in determining whether an event is an important medical event. An important medical event may not be immediately life threatening and/or result in death or hospitalization. However, if it is determined that the event may jeopardize the subject or may require intervention to prevent one of the other AE outcomes, the important medical event should be reported as serious.

### **8.4. Reporting Requirements**

Each AE is to be assessed to determine if it meets the criteria for SAEs. If an SAE occurs, expedited reporting will follow local and international regulations, as appropriate.

#### **8.4.1. Serious Adverse Event Reporting Requirements**

If an SAE occurs, Pfizer is to be notified within 24 hours of investigator awareness of the event

#### **8.4.2. Non-Serious Adverse Event Reporting Requirements**

All AEs will be reported on the AE page(s) of the CRF.

## **9. DATA ANALYSIS/STATISTICAL METHODS**

Detailed methodology for summary and statistical analyses of the data collected in this study will be documented in a Statistical Analysis Plan (SAP). This document may modify the plans outlined in the protocol; however, any major modifications of the primary endpoint definition and/or its analysis will also be reflected in a protocol amendment.

### **9.1. Sample Size Determinations**

Approximately 200 subjects will be enrolled into the trial to provide comprehensive safety data for bococizumab in HIV-infected subjects. Sample size calculations indicate that smaller numbers are required to demonstrate efficacy for the main study endpoints.

The primary endpoint is percent change from baseline to week 12 in fasting LDL-C and the primary comparison of interest is bococizumab 150 mg compared to placebo.

Assuming a dropout rate of 10% for the first 3 months, 54 subjects per treatment group provide more than sufficient power ( $\geq 99\%$ ) to detect expected treatment differences based on the results of a previous study. These calculations are based on  $\alpha=0.05$  (two-sided), a common standard deviation of 25% (based on previous study results), and on

using the normal approximation of the test statistic for the comparison between two means.

## **9.2. Efficacy Analysis**

The full analysis set (FAS) will be the primary analysis set for the analysis of efficacy data in this study. The FAS includes all subjects who were randomized. Subjects will be analyzed according to their randomized treatment group. The comparison of bococizumab to placebo at week 12 is the primary lipid comparison of interest.

The experiment-wise Type I error of  $\alpha=0.05$  (two-sided) for the primary lipid comparison of interest for the primary endpoint and the key secondary lipid endpoints will be controlled by using gatekeeping and Hochberg procedures. Key secondary lipid endpoints will be formally tested only if the null hypothesis for the primary analysis is rejected. The Hochberg procedure will be applied to the key lipid secondary endpoints. All other statistical tests for secondary lipid endpoints will be performed at the two-sided  $\alpha=0.05$  level; no further corrections will be made for multiple endpoints.

### **9.2.1. Analysis of Primary Endpoint**

Percent change from baseline to week 12 in fasting LDL-C by direct method will be analyzed with a mixed model repeated measures (MMRM) approach.

The MMRM analysis is unbiased under data missing at random, a common and plausible scenario in large confirmatory clinical trials. To support the robustness of the conclusions drawn from this analysis, several sensitivity analyses will be performed to explore the dropout pattern and its possible impact on treatment comparisons.

### **9.2.2. Analysis of Key Secondary Endpoints**

Key secondary lipid endpoints include the following:

- Percent change from baseline in fasting TC, non HDL-C, and ApoB at week 12;
- Percent change from baseline in fasting Lp(a) at week 12;
- Percent change from baseline in fasting HDL-C at week 12.

The above key secondary endpoints will be analyzed in a similar manner as the primary endpoint, where an MMRM model will be used.

### **9.2.3. Analysis of Secondary Lipid Endpoints**

Secondary lipid endpoints include the following:

- Percent change from baseline in fasting LDL-C, TC, Apo B, non HDL-C, Lp(a), and HDL-C at week 24;
- Percent change from baseline in fasting TG and ApoA-I at week 12 and week 24;

- Absolute change from baseline in fasting LDL-C, TC, HDL-C, non HDL-C, TG, ApoB, ApoA-I, and Lp(a) at week 12;
- Absolute change from baseline in fasting TC / HDL-C ratio and ApoB / ApoA-I ratio at week 12 and week 24;
- Proportion of subjects achieving fasting LDL-C  $\leq 70$  mg/dL (1.81 mmol/L) at week 12 and week 24;

Endpoints of change and percent change from baseline will be analyzed in a similar manner as the primary lipid endpoint, where an MMRM model will be used.

#### **9.2.4. Analysis of Exploratory Lipid Endpoints**

Exploratory endpoints include the following:

- Proportion of subjects achieving fasting LDL-C  $\leq 50$  mg/dL (1.29 mmol/L) at week 12 and week 24;
- Absolute and percent change from baseline in PCSK9 at week 12 and week 24;
- Plasma bococizumab exposure at week 12 and week 24.

Endpoints of change and percent change from baseline will be analyzed in a similar manner as the primary lipid endpoint, where an MMRM model will be used.

#### **9.2.5. Analysis of the FDG-PET/CT Endpoints**

The main FDG-PET/CT endpoint will be the relative mean change from baseline to 24 weeks in the arterial FDG-PET signal, assessed as a TBR within the most diseased MDS TBR to 24 weeks/end of study will be compared between treatments using an analysis of covariance model including terms for treatment and baseline covariates. The week 24 geometric mean fold change from baseline in the mean of the maximum TBR of segment (MDS) of the index vessel. The week 24 geometric mean fold change from baseline in the mean of the maximum TBR of the MDS will be estimated for each of the two treatment groups and assessed for statistical significance between groups. Data will be log transformed as pre-specified in the Statistical Analysis Plan. Differences between treatments will be assessed based on the observed data values, without adjusting for missing data. Additional sensitivity analyses may be performed using multiple imputation to attempt to correct for any missing data.

The secondary FDG-PET/CT endpoint will be the relative change in the whole vessel TBR within the index vessel.

#### **9.2.6. Analysis of Brachial Artery FMD Endpoints**

The main FMD endpoint is the difference between treatment groups in change in FMD between baseline and 24 weeks. Multivariate models will be constructed to assess the

effect of other variables on change in FMD, including traditional coronary risk factors, statin use, and HIV characteristics including current CD4 count, nadir CD4 count, current use of abacavir, didanosine, tenofovir or protease inhibitors, and duration of antiviral therapy and protease inhibitor therapy.

### **9.3. Analysis of Other Endpoints**

#### **9.3.1. Pharmacokinetics and Pharmacodynamic Data**

If data permit, the following analyses will be performed for plasma bococizumab concentration data and PCSK9 concentration:

- A listing of all plasma PF-04950615 concentrations by patient at nominal time post dose. This listing will also include actual times post dose.
- A descriptive summary of plasma bococizumab concentrations.
- A listing of all plasma PCSK9 concentrations by patient at nominal time post dose. This listing will also include actual times post dose.
- Descriptive summaries for observed PCSK9 concentrations, absolute and percentage change from baseline in PCSK9 concentrations. Summary statistics of arithmetic mean, % coefficient of variation, standard deviation, median, minimum and maximum will be tabulated by study day.

If data permit, plasma bococizumab, PCSK9 and LDL-C concentrations will also be analyzed by ADA status and neutralizing antibody (nAb) status.

### **9.4. Safety Analysis**

Safety will be assessed through adverse and serious adverse events, vital signs, and physical examination, 12-lead ECG recordings, and safety laboratory tests including anti-drug antibodies, hematology, and blood chemistry studies. Unless otherwise specified, safety analyses will be done in the Safety Analysis Set, which is comprised of all subjects who have received at least one dose of randomized study medication. All summaries of safety data will be descriptive only, unless indicated otherwise.

UCSF CHR/HRPP guidelines will be utilized when reporting adverse events. Adverse events, adverse events leading to discontinuation from treatment, and serious adverse events will be tabulated by treatment group. Summaries will also be provided by severity and relationship to study therapy.

Mean observed and mean change from baseline in systolic blood pressure, diastolic blood pressure, heart rate, and weight will be tabulated by visit according to sponsor standards. Observations of potential clinical concern for these parameters will be tabulated according to sponsor standards. Height and temperature will be listed.

Mean observed and mean change from baseline in hematology and blood chemistry parameters will be tabulated by visit according to sponsor standards. Observations of potential clinical concern for hematology and blood chemistry parameters will be

tabulated by treatment group according to sponsor standards. In addition, the proportion of subjects with anti-drug antibodies will be tabulated by treatment group.

12-lead ECGs will be locally read and the interpretations will be kept at the investigation sites as source documents. Any clinically significant ECG abnormalities will be reported as adverse events. Physical examination findings will be listed.

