## **Objectives and Endpoints**

### **Objectives**

The primary objective of the study is to demonstrate the efficacy of LDL-C lowering with bococizumab 150 mg administered subcutaneously every 2 weeks compared to placebo, in HIV-infected subjects whose LDL-C is  $\geq 70$  mg/dL (1.81 mmol/L). The secondary objectives will be to assess the effect of bococizumab compared to placebo on total cholesterol (TC), HDL-C, triglycerides, non-HDL-C, apolipoprotein B (ApoB), apolipoprotein A-I (ApoA-I), and lipoprotein (a) [Lp(a)], and to assess the safety and tolerability of bococizumab.

The study has 3 important tertiary objectives. The first is to determine whether bococizumab compared to placebo improves vascular inflammation in HIV-infected individuals, as assessed by FDG-PET/CT [(18)Fluorodeoxyglucose positron emission tomography/computed tomography]. The second is to determine whether changes in arterial FDG uptake are associated with changes in coronary plaques as measured by CT angiography. The third tertiary objective is to determine whether bococizumab improves endothelial dysfunction among HIV-infected individuals as assessed by flow-mediated dilation of the brachial artery (FMD). We will correlate these findings with changes in LDL-C, inflammatory markers, and Lp(a).

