#### **2.1.2. Secondary Objectives**

The secondary objectives will be to assess the effect of bococizumab compared to placebo on:

- Total cholesterol (TC), HDL-C, TG, and non HDL-C;
- Other lipid parameters, including ApoB, ApoA-I, and Lp(a).

To compare the safety and tolerability of bococizumab 150 mg administered subcutaneously every 2 weeks compared to placebo, in HIV subjects whose LDL-C is  $\geq 70$  mg/dL (1.81 mmol/L).

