### **3. STUDY DESIGN**

This study is a Phase 3, double blind, placebo-controlled, randomized, parallel group study, designed to compare the efficacy and safety of bococizumab 150 mg subcutaneously every 2 weeks to bococizumab placebo subcutaneously every 2 weeks for LDL-C lowering in HIV-infected subjects. The study will enroll approximately 200 subjects in 2 treatment arms, randomized 1:1 to either bococizumab or placebo injections. Randomized subjects will receive study drug for 52 weeks. Rates of discontinuation due to AEs and SAEs will be described for both treatment groups.

After providing informed consent at the screening visit, subjects will be assessed to determine eligibility for the trial. Eligible subjects will be considered enrolled and progress to the Baseline visit. Results from screening evaluations will be reviewed and only subjects who continue to meet all eligibility criteria will be randomized. Randomized subjects will enter the 52-week treatment period, followed by a 6-week follow-up, for a total of 58 weeks study participation. Subjects will attend clinic visits as shown in the Schedule of Activities. Lipid levels will be blinded to the investigator and staff, and subjects.

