#### **5. STUDY TREATMENTS**

Subjects will be randomized into one of 2 parallel groups:

- Bococizumab 150 mg subcutaneously every 2 weeks (n=100);
- Bococizumab placebo subcutaneously every 2 weeks (n=100);

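### Safety versus placebo is a stated objective and the reason for enrolling about 200, but Section 9.4 specifies no between-arm estimate or confidence interval

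*Combined protocol and SAP*

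**What the plan says.** **Objective.** Section 2.1.2 lists as a secondary objective "To compare the safety and tolerability of bococizumab 150 mg administered subcutaneously every 2 weeks compared to placebo". The Objectives paragraph of the Protocol Summary is looser and says "to assess the safety and tolerability of bococizumab".

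**Size.** Section 9.1 states: "Approximately 200 subjects will be enrolled into the trial to provide comprehensive safety data for bococizumab in HIV-infected subjects". It adds that "smaller numbers are required to demonstrate efficacy for the main study endpoints". The Statistical Methods part of the Protocol Summary gives those smaller numbers: 60 per group for LDL-C, 120 in total for FDG-PET/CT, and about 25 per group for FMD. Section 5 allocates 100 subjects to each arm.

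**Analysis.** Section 9.4 states: "All summaries of safety data will be descriptive only, unless indicated otherwise". On events, it says that adverse events, those leading to discontinuation, and "serious adverse events will be tabulated by treatment group". It also provides for summaries by severity and by relationship to treatment, mean changes in vital signs and laboratory values by visit, observations of potential clinical concern, and the proportion with anti-drug antibodies (ADA) by arm. Section 3 is consistent with this: "Rates of discontinuation due to AEs and SAEs will be described for both treatment groups".

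Injection site reactions and Type 1 and 3 hypersensitivity are named safety evaluations in Section 2.2.4, but 9.4 does not mention them separately.

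**The concern.** The objective, the size rationale and the analysis do not quite meet. The objective asks how safety on bococizumab compares with safety on placebo, and the enrolment above the efficacy requirement is there to supply safety data. The analysis sets the two arms side by side and stops. Section 9.4 allows for exceptions to the descriptive rule, but the supplied text contains none for a between-arm safety contrast.

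At stake is how the safety tables can be read. Two similar percentages with 100 subjects in each arm are compatible with a true difference of several points in either direction, and a table without an interval does not show this. Section 9.1 gives alpha, standard deviation, power and dropout for LDL-C. For safety it gives no event rate, detectable difference or precision.

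**Working it through.** **1. The plan's own sample-size figures.** 9.1 gives 54 per group, SD 25%, two-sided alpha 0.05 and 10% dropout. It states no expected difference, so I take the 53.4% reported in Section 1.2.2 for 150 mg every 2 weeks.
- Standard error: 25 × √(2/54) = 4.81.
- 53.4/4.81 − 1.96 = 9.14, so power exceeds 99.99% and the stated figure of at least 99% reproduces.
- Randomized: 54/(1 − 0.10) = 60 per group, 120 in total.
- FDG-PET/CT: 120 × 0.90 × 0.92 × 0.92 = 91.4, in line with the stated 90–92.

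Both calculated requirements stop at 120. The step from 120 to 200 has no calculation to reproduce; the only reason given is safety data.

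**2. Precision of a between-arm difference.** The plan states no safety event rates, so the common rates *p* below are assumptions. Half-width of the 95% interval = 1.96 × √(2p(1 − p)/n).

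| Assumed rate in both arms | n = 60 per arm | n = 100 per arm |
|---|---|---|
| 5% | 7.8 points | 6.0 points |
| 10% | 10.7 points | 8.3 points |
| 20% | 14.3 points | 11.1 points |

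Example: 1.96 × √(2 × 0.05 × 0.95/100) = 0.060. Going from 60 to 100 per arm multiplies the half-width by √(60/100) = 0.77.

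These are Wald approximations. I checked them against Newcombe score intervals with 5, 10 and 20 events of 100 in each arm and obtained ±6.8, ±8.7 and ±11.1 points. The score interval is somewhat wider at low rates; the picture does not change.

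**3. What 100 treated subjects show about a single event type.**
- No events observed: one-sided 95% upper bound 1 − 0.05^(1/100) = 2.95% (with 60 treated, 4.9%).
- Chance of at least one event: 1 − 0.99^100 = 63% at a true rate of 1%; 1 − 0.97^100 = 95% at 3%.

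**4. ADA.** Section 1.2.2 reports 37/517 = 7.2% across completed studies. This pools single- and multiple-dose studies and is not a planning assumption for 52 weeks, so it serves only as an illustration: 7 of 100 has an exact 95% interval of 2.9% to 13.9%.

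**The case against.** The case for leaving 9.4 alone has real weight. Descriptive safety tables by arm are standard, and placing a randomized placebo arm beside the active arm is already a comparison. The plan claims no safety hypothesis, margin or test, so 9.4 fails to deliver nothing that was promised as a test. Detailed methods are deferred to a SAP (opening of Section 9), and the supplied text has no separate SAP, so the intervals may already be planned there. They could also be computed later from the same tables.

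Most of this stands, and it makes the point an improvement and not the correction of an error. It does not remove the gap. A risk difference with an interval is itself descriptive, fits the existing rule in 9.4, and is more useful when its endpoints are chosen before the data are seen.

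Three stronger readings are tempting, and the documents do not support them:
- **That the 80 subjects beyond 120 support no inference.** They belong to the full analysis set (9.2) and so enter the LDL-C model and the Hochberg-tested key secondary endpoints. The Protocol Summary also plans imaging and FMD in all participants, subject to the imaging exclusions in 4.2.
- **That 9.4 offers only counts.** It specifies considerably more, as set out above. Sections 9.2.5 to 9.6 add concentrations by antibody status, a subgroup with low LDL-C, and ongoing review by a monitoring committee.
- **That calling the safety data comprehensive is a false claim.** The word carries no number and can fairly mean breadth of assessment. Step 3 of the check shows the limits for uncommon events, but 9.1 does not claim to exclude them.

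**Conclusion.** The point holds as a proportionate improvement. The plan names a safety comparison with placebo as an objective and cites safety data for its size, yet specifies no between-arm estimate and no measure of uncertainty for it. With 100 per arm that uncertainty is about ±6 to ±11 percentage points for event rates of 5% to 20%, slightly more at the low end with score intervals.

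This rests on assumed rates equal in the two arms, on all 100 subjects per arm contributing, and on the supplied text being all that is specified. The primary LDL-C conclusion, the error control and the enrolment target are unaffected.

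**What to change.** **In 9.4**, pre-specify bococizumab-minus-placebo risk differences with 95% score confidence intervals for:
- any AE;
- any SAE;
- any AE leading to discontinuation of treatment;
- injection site reactions;
- Type 1 and 3 hypersensitivity reactions.

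Report ADA incidence per arm with a 95% confidence interval. Label all of these intervals as descriptive and unadjusted for multiplicity. If a separate SAP already contains them, a cross-reference from 9.4 is enough.

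**Optionally, in 9.1**, state the precision that 100 per arm gives, using the half-widths and the zero-event bound above and marking the event rates as assumptions. It would also be tidy to use one verb for the safety objective in the Protocol Summary and in 2.1.2.

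**Cost.** A few columns in tables already planned and a short change to the protocol text, with no change to enrolment, visits or data collection. The downside is a set of unadjusted intervals that must be read with care: one that excludes zero is a signal to examine and not a confirmed effect, and one that includes zero does not show equal safety.
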